**8. Study Organisation**

**8.1 Sponsor**

This study will be sponsored by the National Waiting Times Centre Board (Golden Jubilee National Hospital).

**8.2 Administration**

All routine clinical and non-clinical co-ordinations of the study will be the responsibility of the Principal Investigator (CH) in conjunction with the research team staff at each site. The Chief Investigator (BS) will assume responsibility for the overall management and conduct of the study.

**8.3 Indemnity**

The NHS research indemnity scheme will apply.

**8.4 Monitoring**

This study will be sponsored by the National Waiting Times Centre Board (Golden Jubilee National Hospital). As such, the Research and Development department will monitor this research in line with the Research Governance Framework for Health and Community Care (Scotland).

**8.5 Funding**

NIAA/VASGBI Trainee Research Development Awarded December 2020.

**9. Ethics and regulatory approval**

The study will be conducted in accordance with the ethical principles of the Declaration of Helsinki. The study will be submitted to a Research Ethics Committee for approval.

**10. Protocol amendments**

Any substantial amendments to the final protocol will be clearly documented and forwarded to the Research Ethics Committee for approval prior to the implementations via the IRAS process of Notification of Substantial Amendment.

**11. Dissemination**

The results of the study will be reported first to study collaborators.

Subsequently, we plan to communicate our results by reporting them to the funder and presentation at national meetings with publication in appropriate peer reviewed journals.

At the end of the study, all participants will be thanked in writing for their participation in the study and will be provided with a short summary of the trial findings. Further details about the trial results and final report will be available on request.

**12. Projected study timetable**

The anticipated duration is 24 months. Set up will take six months from February 2021 and all centres will aim to start recruiting from August 2021, for one year. Follow-up questionnaires will be completed via telephone at three months post-operatively and at one year. We therefore anticipate the dataset for the primary outcome (post-operative myocardial injury) to be complete by August 2022.

**Appendix 1 – ATS Contraindications to exercise testing**

Table 4 Reproduced from ATS Cardiopulmonary Exercise Testing guidelines

Absolute	Relative
Acute myocardial infarction (3–5 days)	Left main coronary stenosis or its equivalent
Unstable angina	Moderate stenotic valvular heart disease
Uncontrolled arrhythmias causing symptoms or hemodynamic compromise	Severe untreated arterial hypertension at rest (> 200 mm Hg systolic, > 120 mm Hg diastolic)
Syncope	Tachyarrhythmias or bradyarrhythmias
Active endocarditis	High-degree atrioventricular block
Acute myocarditis or pericarditis	Hypertrophic cardiomyopathy
Symptomatic severe aortic stenosis	Significant pulmonary hypertension
Uncontrolled heart failure	Advanced or complicated pregnancy
Acute pulmonary embolus or pulmonary infarction	Electrolyte abnormalities
Thrombosis of lower extremities	Orthopedic impairment that compromises exercise performance
Suspected dissecting aneurysm	
Uncontrolled asthma	
Pulmonary oedema	
Room air desaturation at rest $\leq 85\%*$	
Respiratory failure	
Acute noncardiopulmonary disorder that may affect: exercise performance or be aggravated by exercise (i.e. infection, renal failure, thyrotoxicosis)	
Mental impairment leading to inability to cooperate	

\*Exercise patient with supplemental oxygen

## Appendix 2 – Pre-operative Questionnaires

### Quality of Recovery scale – 15

Date: \_\_\_ / \_\_\_ / \_\_\_

Study #: \_\_\_\_\_

Preoperative Postoperative **PART A***How have you been feeling in the last 24 hours?*

(0 to 10, where: 0 = none of the time [poor] and 10 = all of the time [excellent])

1. Able to breathe easily	None of the time	0	1	2	3	4	5	6	7	8	9	10	All of the time
2. Been able to enjoy food	None of the time	0	1	2	3	4	5	6	7	8	9	10	All of the time
3. Feeling rested	None of the time	0	1	2	3	4	5	6	7	8	9	10	All of the time
4. Have had a good sleep	None of the time	0	1	2	3	4	5	6	7	8	9	10	All of the time
5. Able to look after personal toilet and hygiene unaided	None of the time	0	1	2	3	4	5	6	7	8	9	10	All of the time
6. Able to communicate with family or friends	None of the time	0	1	2	3	4	5	6	7	8	9	10	All of the time
7. Getting support from hospital doctors and nurses	None of the time	0	1	2	3	4	5	6	7	8	9	10	All of the time
8. Able to return to work or usual home activities	None of the time	0	1	2	3	4	5	6	7	8	9	10	All of the time
9. Feeling comfortable and in control	None of the time	0	1	2	3	4	5	6	7	8	9	10	All of the time
10. Having a feeling of general well-being	None of the time	0	1	2	3	4	5	6	7	8	9	10	All of the time

**PART B***Have you had any of the following in the last 24 hours?*

(10 to 0, where: 10 = none of the time [excellent] and 0 = all of the time [poor])

11. Moderate pain	None of the time	10	9	8	7	6	5	4	3	2	1	0	All of the time
12. Severe pain	None of the time	10	9	8	7	6	5	4	3	2	1	0	All of the time
13. Nausea or vomiting	None of the time	10	9	8	7	6	5	4	3	2	1	0	All of the time
14. Feeling worried or anxious	None of the time	10	9	8	7	6	5	4	3	2	1	0	All of the time
15. Feeling sad or depressed	None of the time	10	9	8	7	6	5	4	3	2	1	0	All of the time

**EQ-5D-5L**

Under each heading, please tick the ONE box that best describes your health TODAY

**MOBILITY**

I have no problems in walking about   
I have slight problems in walking about   
I have moderate problems in walking about   
I have severe problems in walking about   
I am unable to walk about

**SELF-CARE**

I have no problems washing or dressing myself   
I have slight problems washing or dressing myself   
I have moderate problems washing or dressing myself   
I have severe problems washing or dressing myself   
I am unable to wash or dress myself

**USUAL ACTIVITIES** (e.g. work, study, housework, family or leisure activities)

I have no problems doing my usual activities   
I have slight problems doing my usual activities   
I have moderate problems doing my usual activities   
I have severe problems doing my usual activities   
I am unable to do my usual activities

**PAIN / DISCOMFORT**

I have no pain or discomfort   
I have slight pain or discomfort   
I have moderate pain or discomfort   
I have severe pain or discomfort   
I have extreme pain or discomfort

**ANXIETY / DEPRESSION**

I am not anxious or depressed   
I am slightly anxious or depressed   
I am moderately anxious or depressed   
I am severely anxious or depressed   
I am extremely anxious or depressed

**Appendix 3 – Secondary outcome definitions (alphabetical)**

## 1. Acute Kidney Injury (AKI)

According to the KDIGO consensus definition of AKI:

Stage	Serum Creatinine	Urine output
1	1.5-1.9x baseline OR ≥0.3mg/dL (≥26.5mmol/L) increase	<0.5ml/kg/hr for 6-12 hours
2	2.0-2.9x baseline	<0.5ml/kg/hr for ≥12 hours
3	3.0x baseline OR ≥4.0mg/dL (≥353.6mmol/L) increase OR initiation of renal replacement therapy	<0.3ml/kg/hr for ≥24 hours OR no urine output for ≥12 hours

If urine output is not measured/recorded, incidence of AKI will be solely based on serum creatinine or commencement of renal replacement therapy.

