#### **3.2 Secondary outcome measures**

- Post-operative complications at day 7 based on and including StEP-COMPAC cardiovascular complications, post-operative pulmonary complications, infection, cognitive dysfunction, and acute kidney injury.
- Composite outcomes: major adverse cardiac events (MACE) and major adverse kidney events (MAKE) at days 7 and 30

- Patient-centred outcomes: quality of recovery scale 15 (QoR-15), EQ-5D-5L score, days alive and out of hospital (DAOH) at day 30 and after 1 year
- Clinical indicators: mortality at day 30 and after 1 year, admission to ICU at day 14, readmission to hospital at day 30 and length of hospital stay (with/without in-hospital mortality)
- CPET sub-study: comparison of maximal and submaximal heart rate recovery, plus HRR versus CPET derived indices (AT, VO2peak, and VE/VCO2 at AT). We will also examine patients' perceptions of both tests.

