### 5.3.5 Post-operative clinical data (Full details in Appendix 3)

- Acute Kidney Injury (AKI) as defined by KDIGO consensus at day 7. If urine output is no longer recorded (as not perceived to be clinically necessary), AKI will be scored by serum creatinine only.
- Major Adverse Kidney Events (MAKE) at day 30. MAKE is a composite of ≥30% decline in eGFR at baseline, renal replacement therapy of any duration and renal mortality.
- Infective complications at day 7. These will include presence of fever >38.5°C more than 24 hours following surgery; non-prophylactic antibiotic use and documentation of suspected site (chest/urinary/blood/wound/other). Adapted from StEP-COMPAC outcomes for infection and sepsis.
- Cardiovascular complications at day 7. As per StEP-COMPAC, these include myocardial infarction, cardiovascular death, non-fatal cardiac arrest, coronary revascularisation, PE/DVT and new-onset of atrial fibrillation.
- Major adverse Cardiac Events (MACE) at day 30, day 90 and at 1 year. MACE is a composite of myocardial infarction, non-fatal cardiac arrest, coronary revascularisation and cardiac death.

- Pulmonary complications at day 7, encompassing atelectasis, pneumonia, acute respiratory distress syndrome (ARDS, as defined by Berlin criteria) and pulmonary aspiration.
- Neurological complications at day 7 including 4AT score, and use of anti-delirium medications.
- Admission to ICU at day 14 (or re-admission)
- Days alive and out of hospital at day 30: validated patient-centred outcome that reflects mortality, length of hospital stay, readmissions and discharge to another health facility other than the patient's home.
- All-cause mortality at day 30, 90 and 1 year
- Length of hospital stay +/- in-hospital mortality

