## **7.3 Secondary Outcomes**

Secondary outcomes such as post-operative complications, patient-reported outcome measures, clinical indicators and CPET substudy will be analysed using appropriate statistical methods.

Paired secondary outcomes will be assessed for normality. Comparison will be made using a paired t-test or Wilcoxon signed ranks test. ANOVA or Friedmann's test will be used to assess differences between variables repeated over time. Association will be sought between HRR and appropriate variables using Pearson correlation coefficient or Spearman's rank correlation coefficient as appropriate.

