**5. Major adverse kidney events (MAKE)**

Composite outcome that includes:

- Renal mortality
- Renal replacement therapy of any duration
- ≥30% decline in eGFR from baseline

Measured at a pre-specified time e.g. 30 days after the index operation

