## **Clavien-Dindo scale grading**

All reported postoperative complications will be graded on severity by using the Clavien-Dindo scale:

Grade I	Any deviation from the normal post-operative course not requiring pharmacological treatment or surgical, endoscopic or radiological intervention. This does not include drugs such as antiemetics, antipyretics, analgesics, diuretics, electrolytes and physiotherapy.
Grade II	Requiring pharmacological treatment with drugs other than those described in Grade I. Includes blood transfusions and parenteral nutrition.
Grade III	Requires surgical, endoscopic or radiological intervention
Grade IIIa	Intervention not under general anaesthesia

Grade IIIb	Intervention under general anaesthesia
Grade IV	Life-threatening complication requiring critical care admission
Grade IVa	Single organ dysfunction (not including dialysis)
Grade IVb	Multi-organ dysfunction
Grade V	Death

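### Do the mmol/L creatinine thresholds in the acute kidney injury table put that secondary outcome at risk?

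*Combined protocol and SAP*

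**What the plan says.** AKI is among the day 7 complications listed as secondary outcomes in section 3.2 ("cognitive dysfunction, and acute kidney injury"). Section 5.3.5 refers to the KDIGO consensus and says that, where urine output is no longer charted, "AKI will be scored by serum creatinine only". Appendix 3, item 1, repeats this with one addition: in that case "incidence of AKI will be solely based on serum creatinine or commencement of renal replacement therapy".

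The thresholds appear only in the Appendix 3 table. For stage 1 the creatinine column gives "1.5-1.9x baseline OR ≥0.3mg/dL (≥26.5mmol/L) increase". For stage 3 it gives "3.0x baseline OR ≥4.0mg/dL (≥353.6mmol/L) increase OR initiation of renal replacement therapy". Stage 2 is defined by a ratio to baseline alone.

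On analysis, section 7.3 says only that secondary outcomes "will be analysed using appropriate statistical methods". Under the Clavien-Dindo heading at the end of Appendix 3, "All reported postoperative complications will be graded on severity by using the Clavien-Dindo scale".

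**The concern.** Each bracket offers an SI equivalent of the mg/dL figure beside it, and in the supplied text neither is one. No other section states a creatinine threshold in any unit, so nothing elsewhere corrects the table.

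What could be at stake is the count of AKI cases. The absolute-rise criterion in stage 1 picks up modest rises that stay under 1.5 times baseline. If a derivation were coded with 26.5 mmol/L as its cut-off, no patient could meet that criterion. Patients with such a rise, and without a qualifying urine output record, would be scored as free of AKI.

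**Working it through.** **Inputs.** From the Appendix 3 table: 0.3 mg/dL paired with 26.5, and 4.0 mg/dL paired with 353.6, both brackets in mmol/L as supplied. One figure from outside the document is assumed: a creatinine molar mass of 113.12 g/mol, with 113.0 to 113.2 tried as a range.

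**1. Are the numerals consistent with each other?** The implied conversion factors are 26.5 / 0.3 = 88.3 and 353.6 / 4.0 = 88.4. They agree to rounding, so neither numeral is mistyped.

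**2. Which unit do the numerals fit?** mmol/L = (mg/dL × 10) / molar mass.
- Stage 1: 0.3 × 10 / 113.12 = 0.0265 mmol/L = 26.5 micromol/L.
- Stage 3: 4.0 × 10 / 113.12 = 0.3536 mmol/L = 353.6 micromol/L.

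The plan's numerals are reproduced in micromol/L. Against mmol/L they are too large by factors of 999 and 1000. Across the molar mass range the factor stays between 998 and 1001.

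**3. What would the printed unit mean if taken literally?** 26.5 × 113.12 / 10 = 299.8 mg/dL, and 353.6 × 113.12 / 10 = 3999.9 mg/dL. The literal stage 1 rise would be 299.8 / 4.0 = 75 times the mg/dL rise given for stage 3. The table would contradict its own ordering of severity.

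**4. Who would be misclassified?** Take an assumed baseline of 80 micromol/L and a rise of 30, to 110. The ratio is 110 / 80 = 1.375, below 1.5, so only the absolute criterion can count this patient.
- Worked in mg/dL: 30 / 88.4 = 0.34, which is at least 0.3. Stage 1, correct.
- A micromol/L result set against the printed numeral: 30 is at least 26.5. Stage 1, correct.
- Converted to mmol/L and set against the printed numeral: 0.030 is below 26.5. Missed.

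Only the third route fails. It needs someone to convert into mmol/L on purpose and pass over the mg/dL figure in the same cell. The ratio criteria carry no unit and are unaffected.

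**5. Does the slip reach other outcomes?** The primary outcome rests on troponin (section 3.1), and the sample size on its incidence and an area under the curve (section 7.1). The kidney component of the major adverse kidney events composite is "≥30% decline in eGFR from baseline", a percentage change that uses neither bracket.

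**The case for a change.** The strongest case for acting runs as follows. The table is the only statement of the thresholds, and case report forms are completed by staff at four centres. The formal analysis plan promised in section 7 is still to be written, so a wrong unit could pass into a derivation. If it did, the loss can be described. A rise of 26.5 micromol/L falls short of 1.5 times baseline whenever the baseline exceeds 26.5 / 0.5 = 53 micromol/L. The band of missed rises is then 0.5 × baseline − 26.5 wide: 13.5 micromol/L at an assumed baseline of 80, and 23.5 at 100. A cheap check would remove that risk.

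The mismatch itself stands, and so does this arithmetic, on its condition. The condition is what lacks support: no part of the document derives AKI in mmol/L. The document gives no baseline creatinine values either, so the number of patients cannot be estimated even hypothetically.

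The stage 3 bracket matters less still. A rise of 353.6 micromol/L already reaches 1.5 times baseline at any baseline up to 353.6 / 0.5 = 707.2 micromol/L, so below that it could alter the stage but not whether AKI is counted. Section 7.3 specifies no analysis by AKI stage, though it does not exclude one.

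Nor is it established that the plan contains the slip. A micro sign read as the letter m would produce exactly this pattern: correct numerals and the same wrong prefix twice. Other symbols, such as the greater-or-equal sign, did survive, which tells somewhat against that explanation. However, the degree sign is rendered in two different ways, so symbols were not handled uniformly, and no micro sign appears elsewhere to settle it.

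**Conclusion.** The brackets in the supplied text are wrong by a factor of 1000 in the unit and right in the number. This is a clerical slip in the plan or a fault of text extraction, and the document alone cannot say which. In neither case does the plan need to change. The mg/dL thresholds, the ratio criteria and the KDIGO citation define the outcome without the brackets. The printed numerals also work as they stand for results in micromol/L, and the literal reading is too far from the adjacent figures to be applied unnoticed.

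The expected effect on AKI counts is nil unless someone applies mmol/L literally, and nothing in the document points to that. There is no effect on the primary outcome, the sample size or the composite kidney outcome.

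The conclusion rests on a molar mass of 113.0 to 113.2 g/mol, and on assessors using the mg/dL value or comparing like with like. At most the unit is a proofreading query to settle against the source PDF.

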## 2. Cardiovascular complications

### *Myocardial infarction (MI)*

Acute myocardial injury (20% change in troponin with at least one value above the 99th centile upper reference limit) with clinical evidence of acute myocardial ischaemia, including at least one of:

- Symptoms of myocardial ischaemia
- New ischemic ECG changes
- Development of pathological Q waves
- Imaging evidence of new loss of viable myocardium or regional wall motion abnormality consistent with an ischaemic aetiology
- Identification of coronary thrombus by angiography or autopsy

### *Cardiac death*

Death with a vascular cause, including deaths after an MI, cardiac arrest and cardiac revascularisation procedures. Does not include death after pulmonary embolism, haemorrhage, multi-organ failure or unknown cause of death.

### *Non-fatal cardiac arrest*

Successfully resuscitation from either documented or presumed ventricular fibrillation, sustained ventricular tachycardia, asystole or pulseless electrical activity requiring cardiopulmonary resuscitation, pharmacological therapy or cardiac defibrillation.

### *Coronary revascularisation*

Percutaneous coronary intervention or coronary artery bypass graft surgery within 30 days of index surgery.

### *Pulmonary embolism (PE)*

Requires one of the following:

- High probability ventilation/perfusion lung scan
- Intraluminal filling defect of segmental or larger artery on a helical CT scan
- Intraluminal filling defect on pulmonary angiography
- Positive diagnostic test for deep venous thrombosis (e.g. positive compression ultrasound) plus one of:
  - Non-diagnostic ventilation/perfusion lung scan
  - Non-diagnostic helical CT scan

*Deep venous thrombosis*

Requires one of the following:

- Persistent intraluminal filling defect on contrast venography
- Non-compressibility of one or more venous segments on B-mode compression ultrasonography
- Clearly defined intraluminal filling defect on contrast enhanced CT

*Atrial fibrillation*

New onset of irregularly irregular heart rate in the absence of P waves lasting for at least 30 seconds or for the duration of the ECG recording (if <30s).

**3. Infective complications**

*Fever*

Core body temperature over 38.5°C more than 24 hours following surgery with two readings in a 12 hour period.

*Clinical suspicion of infection*

Use of non-prophylactic antibiotics PLUS documentation of suspected site (respiratory/urinary/blood/wound/other).

**4. Major adverse cardiac events (MACE)**

Composite outcome that includes:

- Cardiac death
- Myocardial infarction
- Non-fatal cardiac arrest
- Coronary revascularisation

Measured at a pre-specified time e.g. 30 days after the index operation

**5. Major adverse kidney events (MAKE)**

Composite outcome that includes:

- Renal mortality
- Renal replacement therapy of any duration
- ≥30% decline in eGFR from baseline

Measured at a pre-specified time e.g. 30 days after the index operation

**6. Neurological complications**

*Delirium screening*

Post-operative delirium is defined as delirium that occurs up to one week post-operatively or up until discharge if earlier than 7 days. A snapshot 4AT test will be performed at day 7 if the patient remains in hospital. A score ≥4 is indicative of delirium.

*Use of anti-delirium medication*

Documentation of any anti-delirium medications given within 7 days postoperatively, including medication and dose given.

*Stroke*

New neurological signs (weakness, expressive/receptive difficulties) lasting over 24 hours or cerebral infarction or intracerebral haemorrhage on computed tomography or magnetic resonance imaging scan.

## 7. Pulmonary complications

Composite of atelectasis, pneumonia, ARDS and pulmonary aspiration as described below:

### *Atelectasis*

Diagnosed on chest radiograph or computed tomography

### *Pneumonia*

Diagnosed using the US Center for Disease control criteria:

- Two or more serial chest radiographs with at least one following feature:
  - New or progressive and persistent infiltrate
  - Consolidation
  - Cavitation
- (One radiograph is sufficient for patients with no underlying pulmonary/cardiac disease)
- AND at least one of:
  - Fever ( $>38.0^{\circ}\text{C}$ ) with no other recognised cause
  - Leukopaenia ( $<4\times 10^9/\text{L}$ ) or leucocytosis ( $>12\times 10^9/\text{L}$ )
  - Altered mental state with no other cause in adults  $>70$  years old
- AND at least two of:
  - New onset of purulent sputum/change in character of sputum/increased respiratory secretions/increased suctioning requirements
  - New onset/worsening cough, dyspnoea or tachypnoea
  - Rales or bronchial breath sounds
  - Worsening gas exchange (hypoxia/increased oxygen requirement/increased ventilator demand)

### *Acute respiratory distress syndrome (ARDS)*

As defined by the Berlin Consensus criteria (2012):

- Within one week of a known clinical insult or new worsening respiratory symptoms
- AND bilateral infiltrates on chest imaging, not fully explained by effusions, lobar/lung collapse or nodules
- AND respiratory failure not explained by cardiac fluid/fluid overload (requires objective assessment)
- AND supplemental oxygenation:
  - Mild =  $\text{PaO}_2:\text{FiO}_2$  26.7-40.0kPa with PEEP or CPAP  $\geq 5\text{cmH}_2\text{O}$
  - Moderate =  $\text{PaO}_2:\text{FiO}_2$  13.3-26.6kPa with PEEP  $\geq 5\text{cmH}_2\text{O}$
  - Severe =  $\text{PaO}_2:\text{FiO}_2 \leq 13.3\text{kPa}$  with PEEP  $\geq 5\text{cmH}_2\text{O}$

